energy intake and both high energy and LA concentration increased the possibility to recover in weight to 2 years of age (OR 30.6, p=0.002). They conclude that “maintaining normal plasma LA for a prolonged period in addition to sustaining a high energy intake may be important in facilitating adequate weight gain” (Shoff et al 2006). These early “responders” also required lower energy intake to maintain adequate growth (Lai et al 2009), which is similar to our observation that patient who received regular LA supplementation had normal weight without increasing the energy intake (Kindstedt-Arfwidson et al 1988). In a follow up study the Wisconsin group found that the early response in growth was associated with better growth and lung function up to 12 years of age and in this paper they also included patients with meconium ileus, who initially had a more severe LA deficiency and they were also later much worse off (Sanders et al. 2018). They summarize that “Further studies are needed to identify optimal CF interventions that can maximize the chance for achieving early growth recovery” (Sanders et al 2018).

People with CF have low IGF-1 concentrations (Switzer et al 2009; Rogan et al 2010; Bessich et al 2013), and the low IGF-I concentrations correlates with lean body mass (Sermet-Gaudelus et al 2003), which usually is low in patients with CF, except in the LA supplied Swedish population (Gronowitz et al. 2008). In transgenic CF rats low IGF-1 levels correlated with impaired growth and bone content (Stalvey et al 2017). Studies have shown that low LA concentrations are associated with low IGF-1 levels in infants (Kjellberg et al 2018) and in animals (Korotkova et al 2004 and 2005). Other factors for poor growth might be an increased caloric demand, and it has been shown that severe CF phenotype is associated with an increased basic

metabolic turn-over (O'Rawe et al 1992). In rats with essential fatty acid deficiency an increased basal respiration has been reported (Rafael et al 1984). Furthermore, the increased intestinal permeability, which relates to membrane phospholipid layers, is correlated to the clinically more severe phenotypes in patients with CF (Hallberg et al 1997).

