Patients with CF, carrying 2 severe mutations referred to Class I and II, i.e. mutations associated with more severe LA deficiency and more severe clinical symptoms, (like delF508, 394delTT) are included after informed consent. The reason for including only those with clinically more severe phenotype is that those have pancreatic insufficiency and also other symptoms more expressively related to genotype (see above). Exclusion criteria will be pregnancy and transplantation and age above 15 and below 5 years (due to pulmonary function tests) and severe liver disease (cirrhosis, portal hypertension). The patients shall not have taken any lipid supplements for 2 months before inclusion and not be treated with any modulators (like Orkambi, Trikafta).

The patients will keep to their ordinary treatment of PERT and vitamins and that for the pulmonary symptoms and infections. No special dietary recommendations will be given, but PERT might be increased, when the supplement is given and that shall be registered. Number of pulmonary exacerbations and type of treatment, including antibiotics, are registered and also compared with the year before the study.

Sample size

A sample of 84 patients (42 per group) will ensure that a two-sided test with α =0.05 has 80% power to detect a 0.5 mean difference in 1-year change in weight-

for-age Z-score, assuming a pooled standard deviation of 0.8. This last figure has been obtained from a previous intervention study on cystic fibrosis patients (Alicandro et al. 2013). Since we expect a withdrawal rate of close to 10%, we planned to enroll 90 patients (45 per groups). The patients and caregivers will be informed by oral and written information and included after informed consent. The study is approved by local Ethic Committees and by the one at Karolinska Institutet and the study is performed according to the Helsinki Declaration.

Design

The study is designed as a double-blind randomized clinical trial

The patients will be randomized to either

- treatment A: linoleic acid (12 g for children 5-15 years) + 600 mg algeal DHA
- treatment B: oleic acid (12 g for children 5-15 years) + 600 mg algeal DHA

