The fatty acids will be given daily for 12 months, in vials containing an emulsion of totally 20 ml (provided by AKK Company, Karlshamn, Sweden and Copenhagen Denmark, packed by WinterMedic, Odense, Denmark), which can be mixed with milk, juice, sour cream, porridge or any similar feeding at breakfast time. Some extra enzymes may be added.

The treatment will last 12 months, starting and ending at time of the yearly check up of the patients. Half the number of patients will be randomly allocated to receive either treatment A or B. An independent researcher (not involved in the study) will generate the allocation sequence at each center. This will reduce small differences in local treatment policy. The vials with supplementation will only be coded (black or white capsula) so neither patient nor caregivers or staff in charge will be informed by the type of supplementation.

Primary Outcome

- BMI Z-score, weight-Z-score

Secondary outcomes

- Height Z-score
- FEV1 (% of predicted) and oxygen saturation
- Exacerbations and infectious parameters compared to year before.
- Plasma phospholipid fatty acid profile.
- Plasma concentration of IGF-I

Explanatory outcomes

- Bone mineral density
- Lean body mass and fat mass.
- Liver function tests
- Lipid mediators (like eicosanoids and docosanoids)
- Cytokines
- 8-iso-prostane
- Sweat sodium and chloride concentrations
- Renal sodium excretion
- Resting energy expenditure
- Intestinal function (fecal calprotectin and fat absorption coefficient)
- Oral glucose tolerance with insulin determination.

METHODS

Patients will be screened for enrollment and will be allocated to one of the treatment at baseline visit. Follow-up visits will be scheduled at 6 and 12 months after treatment allocation. Some measures, like fat absorption coefficient and calprotectin and resting energy expenditure, exhaled NO and ergometer test will not be performed in all patients due to limited capacity at some centres. The study procedures are summarized in table 1.

Table 1. Outline of study procedures

	Baseline visit: Screening and allocation	+6 months	+12 months
Anthropometry	X	X	X
DXA	X		X
FFQ	X	X	X
24-h dietary recall	X	X	X
Pulmonary function	X		X
Blood sample	X	X	X
F-Calprotectin	X		X
Urine sample	X		X
Ergometer test with oxygen saturation	X		X
Oral glucose tolerance	X		X
Indirect calorimetry	X		X
Sweat test	X		X
Compliance to treatment	X	X	X
CF Questionnaire	X	X	X

1. *Anthropometry.*

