Height and weight are controlled with the same equipment for each patient at respective centre and at each scheduled visit (baseline, 6 and 12 months after allocation). Z-scores of weight, height and BMI will be computed using WHO as growth standard. DXA is performed at start and after 12 months period for determination of bone mineral content and density, lean body mass and fat mass.

1. *Food registration.*

- Food frequency questionnaire (FFQ) will be performed at start and each scheduled visit, mainly used for calculation of energy intake and intake of fat and fatty acids (validated questionnaire Eriksson S et al. 2010). Since the products are different in different countries the FFQ form can only suggest **type** of products to be evaluated, complemented by the local dietician. The reason to include these registrations is to individually make a comparison with intake at start and end of study possible, checking that not major changes have occurred in diet, which can influence the results.
- 24-hour recall will be performed at start, 6 months and 12 months after allocation as a complement to FFQ for portion size, type of products etc.

3. *Pulmonary function.*

- Routine pulmonary function (FEV1) at each clinical visit
- Full spirometry at start and end of treatment
- Exhaled NO (if available)
- Ergometer test at start and end
- Oxygen saturation (ear-tip).

4. *Biochemistry.*

- Routine blood biochemistry (fasting) at start and end of treatment period, including Hb, platelets, white blood cell count and differential count, ASAT, ALAT, alkaline phosphatase, GGT, PK, total and conjugated bilirubin, bile acids, cholesterol, lipoproteins, triglycerides, urea, creatinine, glomerulus filtration rate. Ig-G, CRP, sedimentation rate.

- 1 ml serum/plasma for later analyses (to freezer divided in 4 tubes for later analyses of lipid mediators at KI).
- 0,5 ml for IGF-I analysis (to freezer for later analysis in Sweden)
- 0.5 ml plasma for cytokines (to freezer for sending to Stockholm for analyses (OLINK, Uppsala, Sweden).
- 0.5 ml plasma for analyses of phospholipid fatty acids (to freezer for later analysis in Poznan or Stockholm).
- Urine sample for routine tests, incl sodium and creatinine concentrations.

5. *Intestinal function*

- F-Calprotectin at start and after 12 months (in freezer for later analyses at one center)
- Fat absorption at start and 12 months. Three day dietary recording and feces

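### IGF-I, DXA outcomes and resting energy expenditure have no age or sex standardisation and no covariate adjustment in children aged 5 to 15, which costs precision in these secondary and explanatory comparisons

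*Protocol*

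**What the plan says.** Protocol, Patients and Eligibility, excludes "age above 15 and below 5 years (due to pulmonary function tests"), so the eligible range spans ten years. On duration, Protocol, Design, states: "The treatment will last 12 months, starting and ending at time of the yearly check up of the patients".

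Some growth-dependent outcomes are put on a standardised scale. Methods, item 1 (Anthropometry), converts weight, height and BMI to WHO Z-scores, and the secondary outcome list gives FEV1 as a percentage of predicted.

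The others are not. The secondary list has "Plasma concentration of IGF-I". The explanatory list has "Bone mineral density", "Lean body mass and fat mass" and "Resting energy expenditure", with no Z-score, index, percentage of predicted or reference. The Anthropometry item says DXA is done at start and at 12 months for "determination of bone mineral content and density, lean body mass and fat mass", again with no scale for analysis.

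Section 9 (Statistics), worded identically in protocol and SAP, gives secondary and explanatory outcomes a paired t-test or, failing normality, the Wilcoxon signed-rank test. The only further provision is a stratified analysis by sex. Neither document describes adjustment for age or stratification of the allocation by age, and Table 1 has no entry for pubertal stage.

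**The concern.** The plan already treats growth as something to remove from weight, height, BMI and FEV1. IGF-I, bone, body composition and resting energy expenditure also depend on age and growth stage, and every child will grow during the 12 months. A younger and an older child in the same arm can differ in one-year change because of growth stage and not because of the supplement. That spread goes into the standard error unless the analysis accounts for it.

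These outcomes bear on the trial's rationale. The Background links low linoleic acid to low IGF-I and adds that "low IGF-I concentrations correlates with lean body mass". A real effect on them could be missed through avoidable noise. In the one trial that is run, a chance difference in age between arms would be left in the estimate.

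This is separate from the choice of a paired test to compare two independent groups. Replacing that test with an independent-sample test on change would still leave the growth-related spread untouched.

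**Working it through.** **1. The plan's own figure.** The sample size section uses a difference of 0.5, SD 0.8, two-sided alpha 0.05 and 80% power, for change in weight-for-age Z-score.

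- n per arm = 2 × (1.960 + 0.842)² × (0.8/0.5)² = 2 × 7.849 × 2.56 = 40.2, so 41. The t-distribution version gives 41.2, so 42, as stated.
- Power at 42 per arm = Φ(0.625 × √(42/2) − 1.960) = Φ(2.864 − 1.960) = 0.82 (0.81 by the t-distribution).

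This covers weight Z-score only. No SD, growth rate or target effect is given for IGF-I, DXA outcomes or resting energy expenditure, so the rest is a range under assumptions.

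**2. Power lost by not adjusting.** Let R² be the share of the variance of one-year change explained by age, sex and growth phase (assumed). Take an effect of 0.625 adjusted SD, which borrows the planned 0.5/0.8. Without adjustment the SD is larger by 1/√(1 − R²), so power = Φ(2.864 × √(1 − R²) − 1.960). The n per arm for 80% power is 40.2/(1 − R²), rounded up.

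| R² (assumed) | SD inflation | Power, 42 per arm | n per arm for 80% |
|---|---|---|---|
| 0 | 1.00 | 0.82 | 41 |
| 0.10 | 1.05 | 0.78 | 45 |
| 0.25 | 1.15 | 0.70 | 54 |
| 0.50 | 1.41 | 0.53 | 81 |
| 0.75 | 2.00 | 0.30 | 161 |

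**3. What such an R² could look like.** Suppose half the children are in a faster growth phase and their mean annual gain differs by k within-phase SDs (assumed). The variance of change is then 1 + k²/4 times the within-phase variance.

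- k = 1 gives 1.25, so R² = 1 − 1/1.25 = 0.20.
- k = 2 gives 2.0, so R² = 1 − 1/2.0 = 0.50.

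Both lie inside the 0.10 to 0.50 range used for the conclusion. The 0.75 row shows a more extreme case.

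**4. Chance imbalance in age.** With ages uniform on 5 to 15 (assumed), SD = 10/√12 = 2.89 years. The SE of the between-arm difference in mean age is 2.89 × √(2/42) = 0.63, so the 95% range is ±1.96 × 0.63, about ±1.2 years.

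**5. Bias or precision?** In a simulation with no treatment effect (20,000 runs, 42 per arm), both arms were given the same growth drift of 0, 0.25, 0.5 or 1.0 SD of change. A between-arm t-test on change rejected in about 5% of trials at every drift. A paired test read within one arm rejected in 35%, 89% and 100% of trials at the three non-zero drifts. Common growth therefore does not bias a between-arm comparison. It misleads only when the paired test is read arm by arm.

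**The case against.** The case against has several parts, and most of it limits the point without removing it.

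- **Scale.** A reader might infer that all these outcomes will be compared as raw values. The documents do not say so. Bone density, lean and fat mass and resting energy expenditure are listed with no scale at all. Only IGF-I is named as a concentration, and that may describe the assay. What can be said is that no standardisation or adjustment is specified.
- **Size.** A reader might infer that growth swamps any treatment effect. Nothing in the documents shows this, and the table runs from a small loss to a large one. Single 12-month values would look worse: 1 + slope² × (100/12)/SD² gives 3.1 for an assumed 2 units per year with SD 4, and 9.3 for 3 units per year with SD 3. That describes an analysis the plan does not name. The named tests are paired, so they work on within-child change, which removes each child's starting level.
- **Bias.** A reader might infer that age imbalance creates a false effect. Under randomisation, chance imbalance is already reflected in the standard error of a between-arm test, and the false-positive rate stays at about 5%. The harm is lost precision and an uncorrected imbalance in the realised trial.
- **Overlap with the paired-test problem.** Once a between-arm model with baseline is adopted, what remains is the addition of age, sex and height. That is fair, but it still has to be written down, and choosing a different t-test does not supply it.
- **Remedy.** Age, sex and height are only proxies for puberty, so the whole loss cannot be promised back. This stands.

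The planned analysis by sex helps only in part, because it does not address age.

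**Conclusion.** The point holds as a gap in precision for one secondary outcome and several explanatory ones. Section 9 names only tests without covariates for outcomes that depend on growth, and the plan standardises comparable outcomes elsewhere. If age, sex and growth phase explain 10% to 50% of the variance of one-year change, power at 42 per arm for 0.625 adjusted SD falls from 0.82 to between 0.78 and 0.53. Both the R² range and the effect size are assumptions, and the documents allow nothing firmer. The 0.82 is a ceiling that assumes full adjustment for growth.

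Resting energy expenditure will not be measured in every patient, so 42 per arm overstates the numbers available for it. The primary outcome is a Z-score and is unaffected. The change is worth making because it is cheap, but the trial's main conclusion does not depend on it.

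**What to change.** In section 9 of the protocol and SAP, replace the paired tests for IGF-I, bone mineral content and density, lean and fat mass and resting energy expenditure. Compare the arms by linear regression of the 12-month value on treatment, baseline value, age and sex, adding baseline height for body composition, bone and resting energy expenditure. Report the treatment coefficient with its 95% confidence interval. Where a suitable reference is named before unblinding, express IGF-I and bone density as age- and sex-standardised Z-scores.

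No new data are needed. Table 1 schedules the baseline and 12-month measurements and height, and age and sex are already required for the WHO Z-scores. The cost is SAP wording, a regression in place of a simple test, and the choice of a reference for the Z-scores. One limit remains: age, sex and height capture puberty only partly, because pubertal stage is not in Table 1.

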Sampling. Mixture in local laboratory with freezing of an aliquote for later transport to Poznan

6. *Metabolic tests*

- Urine sample for 8-isoprostanate and lipid mediators as eicosanoids, docosanoids and linoleic acid metabolites (directly to freezer -80 each sample in 2 x 8 ml and in 4 x 2 ml) for later analyses in Stockholm.
- Indirect calorimetry at start and after 12 months (if available in the hospital).
- Sweat test at start and after 12 months. **Both sodium** and chloride analyses.
- Oral glucose tolerance test.

7. *Quality of life.*

Quality of life will be assessed through the CF Questionnaire Revised (CFQ), a disease-specific tool that measures health-related quality of life in patients with

CF. There are different versions of the questionnaire: two for children over 6 years, one to be completed by the child and one to be completed by parent (CFQ Child and CFQ-Parent, respectively).

8. Compliance with the treatment

Compliance with the treatment will be evaluated by monthly contact with the study coordinator of respective centre, when not used vials will be registered and new supplied. The patients are asked to make a dairy over the daily intake also reported monthly to the coordinator. Extent of physical activity shall be notified.

9. Statistics

All data will be collected in identical Excel files and analysed in one center at end study.

The main analysis will be carried out on the intention-to-treat population defined as all randomized patients. We will also conduct a secondary analysis on the per-protocol population excluding patients not receiving the allocated treatment for more than 2 months.

Between-treatment differences in the primary outcome across time points will be evaluated by fitting random intercept linear mixed-effects models. Mixed effects model can account for intra-correlated repeated measures on the same subjects and accommodate missing data due to dropouts. The models will include the z-score of BMI as response variable, treatment, time and time x treatment interaction as independent variables. The model coefficients for the time x treatment interaction will be considered an estimate of the treatment effect on changes in the study outcome. Time will be included in the model as categorical variable with the following categories: baseline (pre-treatment), +6 months and +12 months from treatment allocation.

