Secondary and explanatory outcomes will be compared across treatment groups using the paired t-test for normally distributed variables, otherwise the non-parametric Wilcoxon signed-rank test for dependent samples will be used.

A stratified analysis by sex will be performed.

RISK-BENEFIT

There will be no adverse effects to expect of this treatment , since the control group will have the same treatment as offered generally to patients, i.e. extra calories. The extra LA will not exceed the general intake in US (Choque et al 2014). Both groups get similar amount of omega-3 fatty acids; dose in agreement with general recommendations. The extra burden of investigations is small since the patients always have more extensive investigations at the yearly checkup.

IMPORTANCE

If clinical status is improved the patients in both groups will be asked for the possibility to continue with Group A therapy for one further year (requires new ethical applications). Furthermore, good result would indicate a multicenter study for treatment from diagnosis in countries with neonatal screening, which would be extremely important since many of the symptoms start early and especially the supply of high caloric diet gives many problems in patients and parents, and unsatisfying results, It can also have the potential to be a cheap complement to modern expensive drug treatment.

A special benefit for individuals and society would be if this simple, cheap and non hazardous treatment can reduce the enormous costs of the modern drug treatment, which is further not always available.

References:

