## 9. Statistics

All data will be collected in identical Excel files and analysed in one center at end study.

The main analysis will be carried out on the intention-to-treat population defined as all randomized patients. We will also conduct a secondary analysis on the per-protocol population excluding patients not receiving the allocated treatment for more than 2 months.

Between-treatment differences in the primary outcome across time points will be evaluated by fitting random intercept linear mixed-effects models. Mixed effects model can account for intra-correlated repeated measures on the same subjects and accommodate missing data due to dropouts. The models will include the z-score of BMI as response variable, treatment, time and time x treatment interaction as independent variables. The model coefficients for the time x treatment interaction will be considered an estimate of the treatment effect on changes in the study outcome. Time will be included in the model as categorical variable with the following categories: baseline (pre-treatment), +6 months and +12 months from treatment allocation.

Secondary and explanatory outcomes will be compared across treatment groups using the paired t-test for normally distributed variables, otherwise the non-parametric Wilcoxon signed-rank test for dependent samples will be used.

A stratified analysis by sex will be performed.

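### Height Z is recorded at the same three visits as BMI Z but is assigned a two-value paired test; it should have a repeated-measures analysis in all randomised children

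*Protocol*

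**What the plan says.** The protocol's Methods section states "Follow-up visits will be scheduled at 6 and 12 months after treatment allocation", and Table 1 marks anthropometry at all three visits. The Anthropometry paragraph says height and weight are measured "at each scheduled visit (baseline, 6 and 12 months after allocation" and that "Z-scores of weight, height and BMI will be computed using WHO as growth standard". BMI Z and height Z therefore share one schedule and one height reading.

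Section 9, which reads the same in both documents, treats them differently:

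- **BMI Z.** "Between-treatment differences in the primary outcome across time points will be evaluated by fitting random intercept linear mixed-effects models". BMI Z is the only response variable named. The reason given is "Mixed effects model can account for intra-correlated repeated measures on the same subjects and accommodate missing data due to dropouts". On the population: "The main analysis will be carried out on the intention-to-treat population defined as all randomized patients".
- **Height Z.** "Height Z-score" is the first-listed secondary outcome. The rule that covers it is "Secondary and explanatory outcomes will be compared across treatment groups using the paired t-test for normally distributed variables", with the signed-rank test as the alternative. There is no exception for height Z.

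For secondary outcomes the plan does not say which two values form the pair, and gives no rule for missing data.

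**The concern.** The plan's own reasons for the mixed model, repeated measures and dropouts, apply to height Z as much as to BMI Z. Under a two-value test, one of the three visits is unused in any single comparison, and a child lacking either value is lost.

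Three things are at stake. If children leave because of how they grew or tolerated the oil in the first six months, a comparison of those who stay can be biased. BMI Z and height Z would rest on different sets of children, although height is needed to tell whether a BMI change comes from weight or stature. And a paired test run within each arm does not estimate the treatment difference at all.

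Replacing it with an independent-groups test of change would cure only the last of these. The complete-case restriction would remain.

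**Working it through.** **Inputs from the protocol.** 90 enrolled (45 per arm), withdrawal close to 10%, three visits. The sample size of 42 per arm is for 1-year change in weight Z (difference 0.5, SD 0.8, two-sided 5%, 80% power). A two-sample t calculation gives 41.17, rounded up to 42, so that figure reproduces. No figure is stated for height Z. The correlations and SDs of height change used below are therefore assumptions.

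**1. Data used.** Planned heights: 90 × 3 = 270. At 10% withdrawal, 90 × 0.9 = 81 children reach month 12.

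| Analysis | Children | Height values |
|---|---|---|
| Baseline-to-12-month pair | 81 | 81 × 2 = 162 |
| Three-visit mixed model | 90 | 270 − 18 = 252 (all leave before month 6) to 270 − 9 = 261 (all leave after) |

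**2. Precision at 12 months.** This compares the mixed model with complete pairs.

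- No withdrawals: the variance ratio is 1.000. With time categorical, the 6-month height adds nothing to the 12-month contrast.
- All withdrawals before month 6: variance is 0.25% to 3.75% lower (within-child correlation 0.5 to 0.95, compound symmetry or AR(1)).
- All withdrawals after month 6: let r be the correlation of the 6- and 12-month changes. Relative to full data, complete pairs have variance 1/0.9 = 1.111, and using the 6-month value gives 1 + (1 − r²)(0.1/0.9). The ratio is 1 − 0.1r², which is 0.964 at r = 0.6 and 0.919 at r = 0.9, a saving of 3.6% to 8.1%. The compound-symmetry and AR(1) structures above give 2.6% to 5.0%.

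**3. Bias in an adverse case.** Suppose the 10% with the poorest 6-month height change leave one arm only. An independent-groups comparison of completers is then shifted by SD × r × φ(1.2816)/0.9 = SD × r × 0.195, where SD is that of the 12-month change:

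- SD 0.3, r 0.6: 0.035 Z
- SD 0.5, r 0.8: 0.078 Z

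The shift in standard-error units is 0.195r / √(1/45 + 1/40.5), and SD cancels. The two-sided false-positive rate is 8.4% at r = 0.6 and 11.1% at r = 0.8, instead of 5%.

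**4. Which mixed model removes it.** Let k be the SD of the 6-month change divided by that of the 12-month change. The true regression of 12-month on 6-month change has slope r/k. When between-child spread is large relative to the changes, a random-intercept model predicts the missing 12-month value from the average of the baseline and 6-month residuals, which is a slope of about 0.5. The share of bias left is then about 1 − 0.5k/r:

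- r 0.6, k 1.0: 1 − 0.833 = 17%
- r 0.8, k 0.7: 1 − 0.4375 = 56%, or about 0.044 of 0.078 Z
- r 0.8, k 0.6: 1 − 0.375 = 63%

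Large-sample simulated fits (baseline SD assumed 1) agreed with this to within about 6 percentage points. An unstructured covariance left essentially none of the bias.

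**5. Paired tests within arms.** With no treatment effect, 40 children per arm and an assumed change SD of 0.4, exactly one arm was significant in 9% of simulated trials without drift, and in 45% with a common drift of 0.1 Z.

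**The case against.** A reader might infer that the plan prescribes a baseline-to-12-month test and discards every 6-month height. It does not say so. That pair is the natural one, since treatment lasts 12 months and the sample size uses 1-year change, but a separate 6-month test is not excluded. Likewise, a completers-only set follows from the type of test and is not a stated intention. These points stand. Even so, a child without a 12-month height is lost from any two-value 12-month result.

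A reader might also treat height Z as a key outcome. The documents call it secondary, and no power calculation rests on it.

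On size, the unused visit alone costs no 12-month precision, and the two sets of children are nested, 81 within 90. The bias figures require deterministic, one-arm, growth-dependent dropout. Nothing in the documents predicts this, and both arms receive the same gram dose of oil and the same DHA under blinding. All of this stands; the figures show an adverse case and are not a forecast.

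It can be said, too, that the paired test is the graver fault in the sentence and that correcting it would settle height Z. It would do so only if the correction also brought in the 6-month values and the children who leave.

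Finally, one might suppose that copying the primary model across is enough. Step 4 shows that a random intercept removes only part of the bias.

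**Conclusion.** The inconsistency is real and free to correct, and the change should be made. Height Z has the data structure that led the plan to a mixed model for BMI Z, yet it is given a test that uses two values per child and does not itself compare the arms.

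For a baseline-to-12-month comparison at 10% withdrawal, the result rests on about 81 of 90 children. The loss of 12-month precision is 0% to about 8% of variance, according to dropout timing and assumed correlation. The stronger grounds are possible selection bias and poor comparability with BMI Z. In the assumed adverse case the bias is 0.035 to 0.078 Z, with a false-positive rate of 8.4% to 11.1%. The documents do not support presenting that as the expected outcome, nor do they support a claim that the trial's main conclusion is affected.

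**What to change.** In section 9 of both documents:

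- Analyse height Z in all randomised children with a linear mixed model for repeated measures: treatment, categorical time and their interaction, with the 12-month interaction coefficient as the estimate.
- Use an unstructured within-child covariance, not a random intercept alone.
- Apply the same rule to any other continuous outcome that has a 6-month value. Table 1 shows a 6-month blood sample, so plasma fatty acids and IGF-I would qualify if assayed then.
- For outcomes measured only at start and end, replace the paired tests with a between-group comparison of change or a baseline-adjusted ANCOVA.

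The cost is a few sentences and the primary model code with one covariance option changed. No extra visits, measurements or patients are needed.
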